3. STUDY DESIGN

Study design

We will establish a network of community based, NCD surveillance sites in Bangladesh, India North, India South, Pakistan and Sri Lanka (N~40 per geographic region; N~200 in total). Surveillance sites will be centred on primary, community healthcare units, and distributed in representative rural and urban settings. At each of the ~200 surveillance sites, we will carry out systematic, structured assessments of ~750 people from the local, resident adult population (age 18+ yrs), to quantify i. the burden of CVD and T2D, and their risk factors, and ii. the quality of preventative care and disease management for CVD and T2D in the population. Data collection is specifically designed to provide quantitative data on the core NCD surveillance indicators in the WHO Global Monitoring Framework (**Appendix 1**).¹⁶

Data will be collected using shared methodology and standardised operating procedures, and will include measurement of blood based biomarkers for T2D and CVD. Results will be captured electronically to provide a rich and robust resource on ~160,000 men and women from across South Asia, and made available to the health policy makers and other stakeholders to enable assessment of the needs and priorities of the population for NCD prevention and control. In addition biological samples (whole blood, serum and urine) will be collected from the 160,000 people screened to provide a unique and powerful resource for high-quality molecular epidemiological research into the mechanisms underlying, and the biomarkers predicting, the high rates of T2D and CVD in South Asians.

We will continue to monitor the health of South Asians in our surveillance sites long term (>20 years, pending funding), to i. define the prospective relationships between risk factors, biomarkers and incident NCDs, and ii. to document the secular changes in the prevalence of NCD risk factors, and the burden and management of NCDs in the population. The surveillance sites will thus additionally form the backbone of a health observatory system that will additional enable the impacts of health systems and community interventions focused on NCD prevention and control, to be assessed.

Selection of Surveillance sites

We will study at least 40 surveillance sites in each of the 5 study regions (Bangladesh, India North, India South, Pakistan, Sri Lanka; N>200 sites in total). Selection of sites will be done in such a way that we are able to generate credible estimates on burden of CVD and T2D, and their risk factors from a sample that are representative of the country, rural and urban areas separately and for each of the major administrative regions. In outline, site selection for each country/region will be as follows:

Bangladesh. We will select 42 sites, distributed across the entire country (**Appendix 2**). Bangladesh has 8 divisions, with substantial variation in population size between divisions. In addition, the Chittagong Hill Tracts (CHT), which comprise 3 districts, are different from the rest of Bangladesh with respect to population density and ethnicity. We will select 40 surveillance sites from the 8 divisions (excluding the CHT), with the number of surveillance sites in each division being proportionate to the population size of the division. In addition, we will chose a further 2 surveillance sites from CHT (thus N=42 total). The number of rural and urban sites within a division will be proportional to the rural and urban population with a condition that there will be at least 1 urban site in each of the division. The CHT will have 2 rural sites.

The surveillance sites will be selected using a multistage sampling approach. For the selection of rural sites we will randomly select one district from each division and the CHT. We will then randomly select one sub-district from the district/CHT. Afterwards, one or more community clinics (CC) will be selected from the respective sub-district depending on the number of rural sites within the district. The ward in which the CC is located will be our rural surveillance site. For the selection of urban sites, one urban dispensary (UD)/CC will be randomly selected from each of the 12 city corporations. The *mahalla* in which the UD/CC is located will be the urban surveillance site. If the ward/mahalla is too large and has more than 2000 population, we will divide the ward/mahalla into segments. The segment that has the CC/UD will be our surveillance site. Everyone who meets the inclusion criteria within the selected site will be recruited in the surveillance.

India North. We will focus on 40 surveillance sites located in the South Delhi Municipal Corporation (SDMC), in the Delhi National Capital Region (NCR). SDMC serves a population of ~10M people, with diverse demographics characteristics, and includes both urban and rural villages. The South and Najafgrah zones of SDMC will be classified as one hub, while the Central and West zone will be classified as the second hub. We will compile a list of the basic health care units in each SDMC zone (Appendix 2), and classify each as urban / rural based on governmental data. If a health care unit caters to a large population (>50,000), the area will be divided into smaller colonies of 10-50,000 people. From this compiled list of SDMC locations, we will then select 40 surveillance sites at random, but including urban and rural locations in a 1:1 ratio. The population catered to by the health care units will be mobilised by the ASHA workers affiliated to the established surveillance sites.

India South. We will conduct surveillance in both urban and rural areas. The surveillance sites will be villages in rural areas and census enumeration blocks (CEBs) in urban areas. The ultimate stage units will be households in both areas. The rural component of the surveillance is planned to be conducted in 25 selected villages in Cheyur taluk (Appendix 2), which is situated in Kancheepuram district of Tamil Nadu state in southern India. All individuals who meet the inclusion criteria in each household within the selected villages will be invited to participant in the surveillance (n=20,000).

The urban component of the surveillance will be carried out in Chennai, which has a population of 10,705,000 individuals. Chennai is divided into 15 zones and 200 wards by the Chennai Corporation. Of the 200 wards, 40 wards will be randomly selected to represent all 15 zones of the Corporation of Chennai. From the selected 40 wards, 10 Census Enumeration Blocks (CEBs) will be randomly selected from each ward (n=400). The next stage of sampling will be based on systematic sampling where 50 households from each CEB will be selected

with a random start. One individual will be selected using the WHO KISH method and meets the inclusion criteria in each household will be invited to participant in the surveillance (n=20,000) (Appendix 2).

Pakistan. Pakistan has a population of ~214M people, and is divided administratively into four provinces (Balochistan, Punjab, Sindh, Khyber Paktunkhwa) and the Islamabad Capital Territory (ICT). Each province is further divided into divisions, towns and union councils. The union council is the smallest division, and typically consists of ~30,000 people. Each union council has basic health unit and outreach staff. The union council will be our sampling unit for surveillance.

We will focus the surveillance project on the Punjab Province, the most populated state of the country (N=110M). We will aim to establish surveillance sites in each of the 36 states that comprise the Punjab Province, distributed between in proportion to population size, with approximately 1 site per 3 million population. Surveillance sites will be selected using a multistage sampling approach. During the first stage, target towns will be selected for each province, based on population size of the province (one town per 5-6 sites). In each town, the available administrative lists of union councils will be used to select rural and urban union councils in a 1:1 ratio. As stage 1, surveillance will start in central Punjab (Appendix 2), and will be extended to North and South Punjab on successful completion of stage 1.

Sri Lanka. Sri Lanka has 9 Provinces, that are in turn divided administratively into 25 Districts, and then into further administrative units of which the smallest is the Grama Niladhari (GN). We will select 100 surveillance sites from all the districts and provinces. Each site will have 500 persons eligible to be a participant of the surveillance. The number of surveillance sites for each province will be proportionate to the population size of the province. The number of sites for each district within a province will again be proportionate to the population size of the district. Within a district we will allocate the surveillance sites based on the proportion of rural and urban population. The provisional allocation of surveillance sites by district and province is summarized in Appendix 2.

For the selection of rural and urban sites within a district, we will make a list of rural and urban Grama Niladhari (GN) divisions having a Primary Medical Care Units (PMCU) or a Divisional Hospital with a healthy lifestyle center. From the list of these GNs we will randomly select the number of surveillance sites needed for the district. If any GN is too large and has more than 1000 population, we will divide the GN into segments based on already existing demarcations in the electoral lists. The segment that has the PMCU/Divisional Hospitals will be our surveillance site. Everyone who meets the inclusion criteria within the selected site will be invited to be a participant of the surveillance.

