Appendix 2. Draft of proposed surveillance sites

Table 2.1 Bangladesh Sample Design

Selection of rura	l sites			
Division /	District	Sub-district	".00	
Region	(# of sub-	(# of community	# CC	Names of CC
(# of Districts)	districts)	clinics)	selected	
Barisal	Barguna	Betagi	(1)	Talgachhiya Deshantarakathi Cc –Betagi (Code:10002396)
(6)	(6)	(16)	(1)	
				Pathair Cc -saharasthi (Code:10003514)
				Khanesar cc -saharasthi (Code:10003515)
Chittagong	Chandpur	Shahrasti	(6)	Potepur Cc-saharasti (Code:10019104)
(8)*	(8)	(23)		Balshid Cc - Saharasthi (Code:10019229)
	, ,	, ,		Tamta Cc - Shaharasthi (Code:10019230)
				Khampar Cc - Saharasthi (Code:10019233)
				Moulavirchar Cc - Char Bhadrashion (Code:10005146)
				Char Salepur Cc - Char Bhadrashion (Code:10005150)
				Imatmaj Molyar Dangi Cc - Char Bhadrashion
				(Code:10005151)
Dhaka	Faridpur	Charbhadrashan	(8)	Salepur Cc - Char Bhadrashion (Code:10005152)
			(6)	Char Sultanpur Cc - Char Bhadrashion (Code:10005152)
(13)	(9)	(9)		
				Gazirtek Cc - Char Bhadrashion (Code:10005154)
				Joydeb Sarkarer Dangi Cc - Char Bhadrashion
				(Code:10005155)
				Char Jhaukanda CC - Char Bhadrasan (Code:10023641)
Khulna	Kushtia	Daulatpur	(3)	Chatarpara Cc -daulatpur (Code:10008650)
(10)	(6)	(52)	(3)	Kalidaspur Cc -daulatpur (Code:10008651)
(10)	(0)	(32)		Taraguniya Cc -daulatpur (Code:10008666)
Mymensingh	Sherpur	Jhenaigati	(2)	Gojarikura Cc - Jhenaigati (Code:10007335)
(4)	(5)	(22)		Rangamati CC - Jhenaigati (Code:10020689)
	, ,			Rayna Vorat Cc -baraigram (Code:10010109)
Rajshahi	Natore	Baraigram	(4)	Diyar Garfa Cc -baraigram (Code:10010112)
(8)	(5)	(38)	()	Vabanipur Cc -baraigram (Code:10010123)
(-)		()		Borodeha Cc -baraigram (Code:10010131)
			1	Sonapukur Cc - Parbatipur (Code:10011197)
Rangpur	Dinajpur	Parbatipur	(3)	Barakona Cc - Parbatipur (Code:10011198)
(8)	(13)	(40)		Shingimari Darikhamar Cc - Parbatipur (Code:10011228)
Sylhet	Moulvibazar	Sreemangal	1	Grilligiman Bankhamar GC - Farbatipur (GGGE:10011220)
	(7)	(30)	(1)	Sindurkhan Cha Bagan Cc - Sreemangal (Code:10012766)
CHT	Khagrachhari		(2)	Cudu Karbari Dara Ca. Damaarh (Cada 1000 1522)
	•	Ramgarh	(2)	Sudu Karbari Para Cc - Ramgarh (Code:10004532)
(3)	(9)	(11)		Baratholy CC - Ramgarh (Code:10024561)
Selection of urba		Tup/00: :: :	1	
Division	City	UD/CC in the city	N	Names of UD/CC selected
	corporation	corporation		
Barisal	Barisal	35	(1)	Char Karanji Cc - Barishal Sadar (Code:10002513)

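### The 28 rural Bangladesh sites outside the CHT lie in 8 sub-districts, one per division, so the rural part of each division's estimate is unreplicated and Table 4's 0.5% ignores this

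*Protocol*

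**What the plan says.** Protocol section 3 (Selection of Surveillance sites) sets the aim: credible estimates from a sample that is "representative of the country, rural and urban areas separately and for each of the major administrative regions".

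For Bangladesh, 40 sites are spread over the 8 divisions, with "the number of surveillance sites in each division being proportionate to the population size of the division". Two more are added: "The CHT will have 2 rural sites".

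The rural draw has three stages:
- District: "For the selection of rural sites we will randomly select one district from each division and the CHT".
- Sub-district: "We will then randomly select one sub-district from the district/CHT".
- Clinic: "one or more community clinics (CC) will be selected from the respective sub-district depending on the number of rural sites within the district". The text does not say that this last step is random.

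Appendix 2, Table 2.1, headed as a draft, applies the scheme. For Dhaka division, all 8 rural sites are in one sub-district, "Charbhadrashan", which has 9 clinics and lies in one of 13 districts.

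Section 7 plans sample weights for descriptive analysis and mixed models for associations. Table 4 gives a country-level precision of 0.5% for hypertension and for diabetes at 30,000 people.

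**The concern.** Each division is a stratum, and its rural part contains a single first-stage unit. Further clinics in the same sub-district show how clinics differ there. They say nothing about how that sub-district differs from the rest of the division. A peculiarity of the drawn sub-district passes straight into the division's rural figure and cannot be told apart from a real difference between divisions.

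The protocol wants division-level and rural figures to inform health policy, and section 7 intends to explore regional differences within countries. In their rural part, those comparisons would be between sub-districts. Weights and mixed models cannot supply replication that was never sampled. Intervals at the width Table 4 suggests would be too narrow if prevalence varies between sub-districts.

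**Working it through.** **1. Site counts (Appendix 2, Table 2.1)**

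| Division | Districts in division | Sub-district drawn | Rural sites |
|---|---|---|---|
| Barisal | 6 | Betagi | 1 |
| Chittagong (without CHT) | 8 | Shahrasti | 6 |
| Dhaka | 13 | Charbhadrashan | 8 |
| Khulna | 10 | Daulatpur | 3 |
| Mymensingh | 4 | Jhenaigati | 2 |
| Rajshahi | 8 | Baraigram | 4 |
| Rangpur | 8 | Parbatipur | 3 |
| Sylhet | not legible | Sreemangal | 1 |

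Rural sites: 1+6+8+3+2+4+3+1 = 28. Adding 12 urban sites gives 40, and 2 CHT sites (both in Ramgarh) give 42, as section 3 states.

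**2. The plan's own precision (section 7, Table 4)**

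1.96 × √[p(1−p)/30,000] is 0.52% at p = 30% and 0.45% at p = 20%. Both round to the printed 0.5%. The table is thus simple random sampling with no allowance for clustering.

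**3. Effective number of rural sites**

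Allocation is proportional to population, so take division weights W = n/28. Then ΣW² = (1+36+64+9+4+16+9+1)/28² = 140/784 = 0.179. Let ρ be the share of between-site variance (within division) that lies between sub-districts. The effective number is 1/[ρ × 0.179 + (1−ρ)/28].

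| ρ | 0 | 0.25 | 0.5 | 0.75 | 0.9 | 1 |
|---|---|---|---|---|---|---|
| Effective sites | 28 | 14.0 | 9.3 | 7.0 | 6.1 | 5.6 |

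The protocol gives no intra-cluster correlation (ICC) and nothing else that would fix ρ. With CHT, the lower limit is 30²/(140+4) = 6.25.

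**4. Degrees of freedom for between-district variance within division**

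This is the sum over divisions of (districts drawn − 1).
- As planned: 8 × (1−1) = 0.
- One district per rural site: 28 − 8 = 20.
- Two districts in each of the six divisions with two or more rural sites: 6.

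**5. Size in prevalence points**

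Assume a between-sub-district SD within division of 2, 3 or 5 points of hypertension prevalence. This is not in the documents. Half-widths from this component alone, CHT excluded:

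| | Formula | SD 2 | SD 3 | SD 5 |
|---|---|---|---|---|
| Rural only, as planned | 1.96 × SD × √(140/784) | 1.7 | 2.5 | 4.1 |
| Rural only, 28 separate sub-districts | 1.96 × SD/√28 | 0.7 | 1.1 | 1.9 |
| National, as planned (rural weight 28/40) | 1.96 × SD × √(140/1600) | 1.2 | 1.7 | 2.9 |
| National, 28 separate sub-districts | 0.7 × 1.96 × SD/√28 | 0.5 | 0.8 | 1.3 |

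Only the national rows may be set beside Table 4. The SD at which this component alone equals ±0.5 is 0.5/(1.96 × √(140/1600)) = 0.5/0.580 = 0.86 points.

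**The case against.** Several points on the other side stand.

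- A reader might infer that the 28 rural sites carry the information of only about 6. That is the lower limit, reached when nearly all site-to-site variance lies between sub-districts. No ICC is stated, so only the range 5.6 to 28 is supported.
- A reader might infer that representativeness fails outright. District and sub-district are drawn at random and weights are planned. If clinics are also drawn at random, a weighted estimate could be design-unbiased. What is missing is precision and a design-based standard error.
- A reader might set ±0.5 against the rural-only half-widths. Table 4's figure is for the whole country sample, urban and CHT sites included, and the protocol states no rural precision.
- A reader might infer that the analysis will treat the clinic as the cluster. Section 7 does not fix the clustering level, and an analysis plan may properly do so.
- The protocol promises estimates by region and for rural and urban areas separately. It does not promise rural estimates within each division, and division estimates also draw on separately selected urban sites.
- Barisal and Sylhet have one rural site each, so concentration costs nothing there. Appendix 2 is a draft.
- Concentrating sites eases house-to-house listing with local workers, team rotation and long follow-up. That is a legitimate trade-off.

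None of this removes the core. Site selection is fixed in the protocol, and no later analysis can recover variation between districts that were not sampled. The logistical argument is weaker because the same study spreads its Sri Lankan sites over all districts.

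**Conclusion.** The point holds in a limited form. Outside the CHT, rural Bangladesh is observed in 8 sub-districts, one per division. The national rural sample is 30 sites in 9 sub-districts. Between-district variance within a division has no degrees of freedom, so the aim of credible estimates for each major administrative region lacks design support in its rural part. These facts need no assumption beyond Table 2.1 being carried out as drafted.

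The size does rest on assumptions: site shares stand for population shares, and the between-sub-district SD is not documented. Over 2 to 5 points, the component contributes roughly ±1.2 to ±2.9 points to the national hypertension estimate, against a stated total of ±0.5. That total would be exhausted by an SD of about 0.9. The documents do not support calling the sample biased or fixing the effective number at about 6.

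**What to change.** **Preferred, while Appendix 2 is a draft.** Draw the district and sub-district separately for each rural site, or at least draw two districts in each of the six divisions with two or more rural sites. Barisal and Sylhet stay as they are. The printed counts allow even one district per site: Dhaka would use 8 of 13, Chittagong 6 of 8, Rajshahi 4 of 8 and Mymensingh 2 of 4. The numbers of sites and participants are unchanged, but many of the clinics named in Table 2.1 would be replaced. The cost is more travel, more local approvals and more scattered listing and follow-up.

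**If the present draw is kept**, three changes to wording and analysis are needed:
1. State in section 3 that each division's rural component represents one sub-district.
2. Restate the Bangladesh country-level precision in Table 4 with a design effect over an assumed ICC range.
3. Estimate variance with sub-district as primary sampling unit and collapsed strata. Pairing the eight divisions leaves 4 degrees of freedom. Say that this is conservative, because true differences between paired divisions enter the variance.

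This fallback costs no fieldwork, but it does not restore the missing replication.

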4. PARTICIPANT ENTRY

Participants: entry criteria and sample size

All adults South Asian men and women living within the geographic boundaries of the selected surveillance site (as described by the relevant national administrative systems), will be invited to take part in the research. Recruitment targets (participants with appropriate consent, data and samples collected) by region to 2021 are provided in **Table 1**.

Inclusion criteria will be:

- 1. Age 18+ years
- 2. Male or Female
- 3. South Asian ancestry
- 4. Permanent resident of the surveillance site (resident for >12 months)

Exclusion criteria will be:

- Planning to leave the study site within the next 12 months
- Cancer or other serious illness expected to reduce life expectancy to less than 12 months

· Unable or unwilling to give consent

Table 1. Recruitment targets by country / region for the Surveillance study.

Region	Recruitment target	Partner organisations
Bangladesh	30,000	BRAC University, Dhaka
North India	30,000	DDF (Max Healthcare), Delhi
South India	40,000	Madras Diabetes Research Foundation, Chennai
Pakistan	30,000	Service Institute of Medical Science, Lahore Punjab Institute of Cardiology, Lahore King Edward Medical University, Lahore
Sri Lanka	30,000	University of Colombo, Colombo University of Kelaniya, Ragama

Recruitment

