At each study site, governmental census data and other available household listings will be used, supported by house-house visits, to fully enumerate and identify the resident population. House-to-house visits will be done by the local primary care worker, in partnership with the research team. The purpose and potential benefits (personal and societal) of the surveillance will be explained. The research team will then obtain demographic details for the adult population of each household. People eligible and consenting to take part in the surveillance study will be asked to attend a nearby health facility in the fasting state, for the surveillance health assessment. Explanations of the project will be provided in writing and using videos, available in relevant South Asian languages, and supported by bilingual translators. We will also engage the community elders (eg teachers, employers, religious leaders) as trusted third parties, to support and facilitate engagement of the community in the study. Based on previous experience with population studies in these communities, participation rates are expected to exceed >70%; the availability of household enumeration data will enable participation to be monitored in detail, including by age, gender and major socio-economic groups.

Study procedures

Participants will be asked to attend in the morning after an overnight fast (water only after midnight). All participants will complete a structured assessment by trained members the dedicated research team, in five complementary domains: i. Registration and consent; ii. Questionnaire; iii. Physical measurements; iv. Biological samples and v. Clinical reporting. All study procedures implemented represent well established tools, that are validated for assessment of NCDs in population studies. The procedures will be carried out by trained research staff, using equipment and protocols that are standardized between countries and surveillance sites.

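### India North and Pakistan: no selection stage is stated below sites that can hold tens of thousands of people, so how about 750 per site are chosen, and with what probability, is undefined for 60,000 of 160,000 participants

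*Protocol*

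**What the plan says.** Section 3 (Study design) sets the workload per site: "we will carry out systematic, structured assessments of ~750 people from the local, resident adult population". With at least 40 sites per region, this matches the Table 1 targets of 30,000 for North India and 30,000 for Pakistan.

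The India North paragraph limits only how large a site may be: "If a health care unit caters to a large population (>50,000), the area will be divided into smaller colonies of 10-50,000 people". The last random step follows: "we will then select 40 surveillance sites at random, but including urban and rural locations in a 1:1 ratio". The paragraph closes with recruitment: "The population catered to by the health care units will be mobilised by the ASHA workers affiliated to the established surveillance sites".

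The Pakistan paragraph says "The union council is the smallest division, and typically consists of ~30,000 people" and then "The union council will be our sampling unit for surveillance". Towns are chosen, then rural and urban union councils in equal numbers. Nothing is stated below the union council.

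Section 4 (Participant entry) extends the invitation to "All adults South Asian men and women living within the geographic boundaries of the selected surveillance site". Its Recruitment text says "participation rates are expected to exceed >70" per cent, and promises full enumeration of residents through listings and house-to-house visits. Section 7 says that sample weights will be estimated because the sampling is multistage.

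The other regions do state their last step. Bangladesh segments sites above 2,000 people and Sri Lanka above 1,000, and each then takes everyone eligible. Rural South India invites everyone eligible in the selected villages. Chennai draws households systematically from a random start and picks one person per household by the Kish method.

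**The concern.** Three statements meet in the same site: everyone is invited, most come, and about 750 are assessed. In a site of a few thousand people or fewer they can be reconciled. In a colony of 10,000-50,000 or a union council of 30,000 they cannot. Someone in the field has to decide which adults make up the 750, and the protocol gives no rule.

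Two things are at stake. A design weight is the inverse of a known inclusion probability. If the last stage has no defined probability, the weight in Section 7 has no defined value, however carefully the sites themselves were drawn. In addition, Sections 2 and 3 claim a representative sample. That claim depends on how people are picked within the site, and a larger sample does not repair an undefined selection. Who is approached is settled in the field, so a later analysis plan cannot restore it.

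**Working it through.** **Inputs from the protocol.** Number assessed per site, about 750 (Section 3). Sites, at least 40 per region (Section 3). Targets, 30,000 for North India and 30,000 for Pakistan (Table 1). Participation, taken as 0.70, the lower end of what is expected (Section 4). Site size, 10,000-50,000 for split North India units and typically 30,000 for a union council (Section 3).

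**Assumption.** The share of residents aged 18 or over is not given. I use a range of 60-70%. Exclusions for short residence, planned departure or serious illness are also not quantified and are ignored.

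**Step 1: the plan's own figures.**
- 30,000 / 40 = 750 per site.
- Table 1 total: 30,000 + 30,000 + 40,000 + 30,000 + 30,000 = 160,000.
- Table 4, site level, 30% prevalence: 1.96 × √(0.30 × 0.70 / 750) = 3.28%, stated as 3.3%. The planned 750 is therefore used consistently, with a simple random sampling formula.

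**Step 2: attendance if all adults are invited.** Attenders = residents × adult share × 0.70.

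| Residents in site | Adults (60-70%) | Attenders | Multiple of 750 | 750 as share of adults |
|---|---|---|---|---|
| 10,000 | 6,000-7,000 | 4,200-4,900 | 5.6-6.5 | 10.7-12.5% |
| 30,000 | 18,000-21,000 | 12,600-14,700 | 16.8-19.6 | 3.6-4.2% |
| 50,000 | 30,000-35,000 | 21,000-24,500 | 28.0-32.7 | 2.1-2.5% |
| 2,000 (Bangladesh cap) | 1,200-1,400 | 840-980 | 1.1-1.3 | 53.6-62.5% |

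The last row is a check: at the Bangladesh cap the same three statements nearly agree.

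**Step 3: site size at which they agree.** 750 / 0.70 = 1,071 adults to invite. Dividing by the adult share gives 1,071 / 0.70 = 1,530 to 1,071 / 0.60 = 1,790 residents (rounded). Sites well above that size need a further stage.

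**Step 4: capacity.** Section 6 expects about 60,000 assessments a year over all regions. Forty union councils would produce 40 × 12,600 = 504,000 to 40 × 14,700 = 588,000 attenders, or 8.4 to 9.8 years of the whole programme. Assessing everyone who accepts is not a feasible reading.

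**Step 5: sensitivity to the number of Pakistan sites.** One site per 3 million of 110 million gives 110 / 3 = 36.7 sites and 30,000 / 36.7 = 818 per site. The multiple is then 12,600 / 818 = 15.4 to 14,700 / 818 = 18.0, and the conclusion is the same.

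**Step 6: share of the study affected.** (30,000 + 30,000) / 160,000 = 37.5%.

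**The case against.** The strongest reply is that the protocol does not describe a free-for-all. Section 4 promises enumeration of all residents and house-to-house visits, and Table 2 gives every team household listing as an afternoon task. Mobilisation by health workers in India North can be read as those same visits. This stands. A reader might infer that the first 750 or so who turn up are taken, or that these regions become a volunteer sample. The protocol says neither. It supports only that selection within the site is unspecified and not stated to be random.

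Nor does it follow that no weights could be computed at all. Enumeration, with participation monitored by age, gender and socio-economic group, would permit post-stratification. But that rests on a model, namely that assessed adults resemble the others within each stratum. It does not supply the missing design probability.

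A reader might also want to attach a bias of several percentage points. The documents give no difference between assessed and unassessed adults, so no bias figure can be supported.

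Site size is a fair objection too. The 10,000-50,000 range applies only to North India units that are split; unsplit units have no stated floor. Table 2.2 in Appendix 2 names draft areas without populations, and some names suggest small settlements. The Pakistan figure is a typical value, site selection is described only in outline, and the site visit plan for Pakistan is a figure not reproduced in the text available. If actual sites are near 2,000 residents, the conflict disappears there. The text should then say so, because the sizes that it does state produce the conflict.

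Finally, Bangladesh and Sri Lanka are not a model of random selection within the site: both keep the segment that holds the clinic. They show that the last step can be written down, not that it is drawn at random.

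**Conclusion.** The point holds as a conflict within the protocol and a gap in the sampling design. For the site sizes stated for India North and Pakistan, inviting all adults, expecting more than 70% participation and assessing about 750 per site differ by a factor of about 6 to 33. No stage below the site is stated that would resolve this. Last-stage inclusion probabilities, and with them the design weights in Section 7, are undefined for 60,000 of 160,000 participants (37.5%).

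The size of the mismatch rests on an assumed adult share of 60-70%, on 70% participation, and on sites being as large as the text says. The adult share does not drive the conclusion. The actual site size does: the count of 60,000 includes any unsplit North India units and smaller union councils that may turn out to be near 2,000 residents. The direction and amount of any bias cannot be judged from the documents.

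**What to change.** For India North and Pakistan sites much larger than about 2,000 residents, add a final probability stage, by one of two routes:

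- **One segment drawn at random.** About 1,530-1,790 residents, similar in size to the Bangladesh cap, but drawn at random and not fixed as the segment containing the clinic. Everyone eligible in it is invited.
- **A systematic household sample with a random start**, as in Chennai. The fraction of adults invited would be about 15-18% in a site of 10,000 (1,071 / 7,000 to 1,071 / 6,000), 5-6% at 30,000 and 3-4% at 50,000.

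Either route is sized to invite about 1,070 eligible adults per site (750 / 0.70), slightly more if exclusions are common. Record the selection probability for each site, and the number of eligible adults per household if only one is taken. Amend Section 4 so that the invitation to all adults refers to the selected segment or households. State the populations of the North India areas in Table 2.2, so that it is clear which sites need the extra stage.

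The cost is protocol wording and one random draw per site, plus call-backs to selected households. A single segment adds some clustering. Systematic sampling needs a household frame for the whole site. Listing shrinks only with the segment option: in Pakistan from 40 × 30,000 = 1,200,000 residents to 40 × 1,530 = 61,200 up to 40 × 1,790 = 71,600.
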